5.4.4 Analysis of Secondary endpoints

The secondary analyses will consist of:

- Evolution of VAS from the day (D0) of use of Alveogyl to 7 days post treatment. Summary statistics of VAS will be provided at Day D0, D3, D5 and D7 in available observations (no imputation for missing values will be made). For each timepoint, difference with measure at D0 will also be calculated.
- The complication rate will be calculated: number and proportions of the events (quoted in §1.5.2) occurring post treatment
- Description of the clinical signs at D7 and at intermediary visits (if any) to measure the impact of Alveogyl treatment on healing, on antiseptic effect, on local inflammation, and on hemostasis: number and proportions.
- The use of painkillers at D3 and at D7 will be described.
- A listing of the adverse events (AE) will be provided organized by type of AE (Adverse Event ; Adverse Effect related to Alveogyl ; Deficiency of Alveogyl ; Other type or Unknown)

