1.5.2 Anticipated adverse events related to device or procedure

The following possible adverse events related to the device or to the procedure of dry socket treatment have been identified during clinical evaluation and risk analysis:

- Mouth ulceration,

- Pain,
- Paresthesia,
- Infections (osteitis, abscess),
- Swelling,
- Hypersensitivity/irritation reactions
- Local inflammation,
- Temporary fever,
- Bleeding gum,
- Delayed healing,
- Possible increased bone resorption (the material should be removed in the area that receives future implants),
- Ulceration.

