3.1.2 Secondary objectives

To measure the impact of Alveogyl treatment on painkiller intake.

To measure the impact of Alveogyl treatment on healing.

To measure the impact of Alveogyl treatment on local inflammation.

To measure the impact of Alveogyl treatment on antiseptic effect.

To measure the impact of Alveogyl treatment on hemostasis.

To measure the safety and complication rate of Alveogyl treatment.

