3.2.2 Secondary endpoints

Painkiller intake: Analgesic use [Time Frame: at 3 days, 5 days and 7 days post-treatment]

Healing: Evaluation of healing of the alveolar mucosa. [Time Frame: at 7 days post-treatment].

Local inflammation: Signs of inflammation around the gingival mucosa (oedema, redness, sensitivity) [Time Frame: at 7 days post-treatment].

Antiseptic effect: Clinical signs (e.g., gum pain, swollen gum lining, fever, halitosis). [Time Frame: at 7 days post-treatment].

Hemostasis: presence or absence of bleeding [Time Frame: after Alveogyl placement].

Safety: Complication rate [Time Frame: From Alveogyl placement to 7 days post-treatment]

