Unanticipated Serious Adverse Device Effect (USADE) (ISO14155)

Serious adverse device effect (SADE) which by its nature, incidence, severity or outcome has not been identified in the current version of the risk analysis report.

Device deficiency with Serious Adverse Device Effect (SADE) potential ((Art. 80 §1 c) MDR; ISO14155)

Any device deficiency that might have led to a serious adverse event if appropriate action had not been taken, intervention had not occurred, or circumstances had been less fortunate.

Serious incident: (Art. 2 § 65MDR)

Means any incident that directly or indirectly led, might have led or might lead to any of the following:

- (a) the death of a patient, user or other person,
- (b) the temporary or permanent serious deterioration of a patient's, user's or other person's state of health,
- (c) a serious public health threat;

Serious public health threat: (Art. 2 § 66MDR)

Event which could result in imminent risk of death, serious deterioration in a person's state of health, or serious illness, that may require prompt remedial action, and that may cause significant morbidity or mortality in humans, or that is unusual or unexpected for the given place and time.

Causal Relationship of SAE (MDCG 2020-10/1)

A causal relationship towards the medical device or the procedure of the investigation should be rated by the PI and the Sponsor as follows:

- e) Not related: The relationship to the device or procedures can be excluded.

- f) Possible: The relationship with the use of the investigational device is weak but cannot be ruled out completely. Alternative causes are also possible.
- g) Probable: The relationship with the use of the investigational device seems relevant and/or the event cannot reasonably be explained by another cause.
- h) Causal relationship: The serious event is associated with the investigational device or with procedures beyond reasonable doubt.

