6.2 SAFETY DATA RECORDING

From the "Visite 1 - Day 0" date until patient end of study (i.e., withdrawal/end of follow-up/lost to follow-up), all adverse events (serious and non-serious), exposure during pregnancy and device deficiencies that occur will be fully investigated, recorded and classified by the Investigator in line with the definitions provided in the norm ISO14155:2020 and guideline MEDDEV 2.7/3.

Investigators will check patients file during clinical follow-up visit and ask patients if they experienced any complications since the index procedure / last visit.

Safety data will be reported in the Case Report Form.

Documentation of AEs (including SAEs) by the PI includes diagnosis or symptoms, start and stop dates of event, event treatment, event resolution, assessment of seriousness and causal relationship to Medical Device and/or investigation procedure (ISO14155).

Documentation of DDs by the PI includes description of event, start date, investigational device information, action taken with regard to the investigational device, and whether the DD led to an AE. The Sponsor shall review all DDs and determine and document in writing whether they could.

The Sponsor provides the Competent/Regulatory Authority (CA/RA) (if applicable) and the Ethic Committee (EC/IRB) with the documentation at their request.

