6.4 ADVERSE EVENTS CATEGORIZATION

The adverse events are categorized by the PI and the Sponsor using the following algorithm:

Does the AE meet the seriousness criteria?

1. No, it is not serious

Is the relationship to the device or the procedure possible, probable or causal?

- No: non-related AE
- Yes: ADE

2. Yes, it is serious: SAE

Is the relationship to the device or the procedure possible, probable or causal?

- No: non-related SAE
- Yes: SADE

Is it anticipated (within expected type, severity and frequency of the complications)?

1. No: unanticipated SADE (USADE)
2. Yes: anticipated SADE (ASADE)

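### Adverse events outside the section 1.5.2 list enter no planned adverse-event proportion, although section 6.2 records every adverse event and safety is a stated objective

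*Combined protocol and SAP*

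**What the plan says.** The safety objective in section 3.1.2 is "To measure the safety and complication rate of Alveogyl treatment". The matching endpoint in section 3.2.2 reads "Safety: Complication rate [Time Frame: From Alveogyl placement to 7 days post-treatment" and refers to no list of events.

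Collection is broad. Under section 6.2, "all adverse events (serious and non-serious), exposure during pregnancy and device deficiencies that occur will be fully investigated, recorded and classified". The record for each AE includes "start and stop dates of event, event treatment, event resolution, assessment of seriousness and causal relationship". Section 6.4 then sorts every AE by seriousness, relatedness and, for serious related events, whether it was anticipated.

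The analysis is narrower. Section 5.4.4 defines the complication rate as the "number and proportions of the events (quoted in §1.5.2) occurring post treatment". Section 1.5.2 introduces its list by saying that these "possible adverse events related to the device or to the procedure of dry socket treatment have been identified during clinical evaluation and risk analysis". It has 12 bullets (ulceration appears in two of them) and no category for other events. The only other AE output in section 5.4.4 is a listing by type, with no count, percentage or denominator attached.

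Section 5.4 gives a general rule that qualitative data are shown with percentages, and announces a separate SAP, which is not in the supplied text.

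**The concern.** The objective, the endpoint and the data collection are not tied to events foreseen in advance; the analysis rule is. A safety summary built on a list of foreseen events is least informative about the unforeseen ones, and those are part of what a safety objective should bring out. In India the study is treated as pivotal, and section 1.1 says it is meant to confirm safety as well as performance. Followed as written, section 5.4.4 would give a reader a proportion for the expected complications and, for every other AE, only lines in a listing.

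**Working it through.** **Plan's own figure.** The documents state no safety rate and no expected AE frequency, so there is no safety figure to reproduce. The one design figure, 113 evaluable patients, belongs to the primary endpoint. It reproduces as 1.96² × 0.92 × 0.08 / 0.05² = 113.09 and plays no part here.

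**Step 1: is the list complete against the protocol's own safety text?** Section 1.5.3 names five reported concerns. Compared with section 1.5.2:

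- paresthesia: on the list
- pain: on the list
- irritation: on the list (shared bullet with hypersensitivity)
- hypersensitivity: on the list
- dysaesthesia: not on the list

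So four of five match. Read literally, a patient whose only event is dysaesthesia does not count towards the complication rate.

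**Step 2: does another planned output give off-list AEs a proportion?** Going through section 5.4.4:

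- VAS summaries and painkiller use are not AE outputs.
- Clinical signs at Day 7 and at intermediate visits are given with numbers and proportions. Section 3.2.2 names halitosis among such signs, and halitosis is not in section 1.5.2, so it gets a proportion. The stated purpose is to describe healing, antiseptic effect, inflammation and hemostasis, not AE incidence.
- The AE listing covers all AEs, but only as a listing.

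No AE, ADE, SAE, SADE or USADE proportion is planned, although section 6.4 creates those categories.

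**Step 3: unanticipated effects.** Section 6.1 defines a USADE as a serious device effect "which by its nature, incidence, severity or outcome has not been identified in the current version of the risk analysis report". An effect unanticipated by incidence, severity or outcome may still carry a listed term and be counted. One unanticipated by nature would tend to fall off a list of anticipated events. The reference is the risk analysis report, whose content (Annex 2) is not in the supplied text, so its match with section 1.5.2 cannot be checked.

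**Step 4: size.** Assume a per-patient rate. Let N be the number of treated patients, a the number with at least one listed event, and b the number with off-list events only.

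- Listed-event rate = a/N
- Any-AE rate = (a + b)/N
- Difference = b/N, whatever a is

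With N = 120 (planned enrolment, section 4.2.3), one such patient gives 1/120 = 0.83 percentage points. The documents give no value for b. For assumed values of 1, 3 and 6 the difference is 0.83, 2.5 and 5.0 points; with b = 0 there is none.

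**The case against.** The strongest reply is that the endpoint is a complication rate, not an any-AE rate. Defining complications is the proper job of an analysis section, and leaving unrelated events out of such a rate is reasonable. This stands: the two rates are different quantities, and a correctly labelled listed-event rate is not biased because it differs from an any-AE rate. It does not settle the matter, because section 3.1.2 names safety as well as the complication rate, and related off-list events are left out along with unrelated ones.

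Second, nothing is lost. Off-list AEs are recorded, categorised, reported and listed, and with 120 patients followed for about a week a reader could count them from the listing. This also stands, but it leaves the count, the unit and the denominator to each reader.

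Third, the general percentage rule in section 5.4 or the separate SAP might supply AE percentages. They might. The general rule does not name AEs, section 5.4.4 specifically assigns them a listing, and nothing supplied commits to an incidence table.

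Fourth, the list is broad and the size is unknown. Both are true. Section 5.4.4 also states no unit or denominator, so the 0.83-point figure holds only on a per-patient reading over 120.

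**Conclusion.** The point holds in a limited form. By a stated rule, AEs outside section 1.5.2 enter no planned adverse-event proportion, although all AEs are collected and safety is an objective. Dysaesthesia is an example from the protocol's own text. The consequence is confined to a descriptive secondary summary; no test, sample size or primary result changes. Its size cannot be derived from the documents. It is 0.83 points per patient with only off-list events, assuming a per-patient rate over 120.

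Stronger readings that a reader might infer are not supported:

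- That the complication rate understates the AE rate. It does not claim to estimate that rate.
- That off-list events are lost or appear in no proportion at all. They are listed, and halitosis, for one, is summarised as a clinical sign.
- That every USADE is left out. Only those unanticipated by nature are likely to be, and Annex 2 cannot be checked.
- That pain, inflammation or swelling already present at Day 0 would be counted as complications. Section 5.4.4 does not spell this out, but its restriction to events after treatment, the relatedness wording of section 1.5.2 and the recorded start dates point to new events.

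**What to change.** In section 5.4.4, or in the separate SAP:

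- Keep the complication rate based on section 1.5.2, labelled as a subset of all AEs.
- Add the number and percentage of treated patients with at least one AE of any term from Alveogyl placement to Day 7.
- Add the same for patients with at least one device- or procedure-related AE.
- Break these down by the section 6.4 categories.
- State that the unit is the patient and the denominator is all treated patients. Exact 95% confidence intervals are optional.

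The cost is a short addition to the text and one extra table. Start dates, seriousness and causality are already recorded for each AE under section 6.2, so no new data are needed. The downside is that the any-AE figure includes events unrelated to the device or procedure; the related-AE row separates them.

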5.4.5 Interim analyses

N/A. No interim analysis is planned.

5.4.6 Deviation(s) from the original statistical plan

If any, additional analyses or changes from the initial plan will be described in the study report.

5.5 HANDLING OF MISSING DATA AND DROP-OUTS

No data will not be imputed, only available data will be used in the analyses.

6 SAFETY MANAGEMENT

6.1 DEFINITIONS

For sake of clarity, the source of each definition wording is given between brackets.

Adverse Event (AE) (Art. 2 §57 MDR)

Any untoward medical occurrence, unintended disease or injury or any untoward clinical signs (including an abnormal laboratory finding) in subjects, users or other persons whether or not related to the Medical Device.

Adverse Device Effect (ADE) (ISO14155)

Adverse event possibly, probably or causally related to the use of an investigational device or procedures.

Use error (ISO14155)

User action or lack of user action while using the medical device that leads to a different result than that intended by the manufacturer or expected by the user

Incident (Art. 2 §64 MDR)

Any malfunction or deterioration in the characteristics or performance of a device made available on the market, including use-error due to ergonomic features, as well as any inadequacy in the information supplied by the manufacturer and any undesirable side-effect

Malfunction (ISO14155)

Failure of an investigational device to perform in accordance with its intended purpose when used in accordance with the instructions for use or the CIP.

Device deficiency (Art. 2 §59 MDR)

Inadequacy of a medical device related to its identity, quality, durability, reliability, safety or performance, of an investigational device, including malfunction, user errors and inadequate information supplied by the manufacturer.

Serious Adverse Event (SAE) (Art. 2 §58 MDR)

Any adverse event that led to any of the following:

- (a) death,
- (b) serious deterioration in the health of the subject that resulted in any of the following:
 - (i) life-threatening illness or injury,

- (ii) permanent impairment of a body structure or a body function,
- (iii) hospitalisation or prolongation of patient hospitalisation,
- (iv) medical or surgical intervention to prevent life-threatening illness or injury or permanent impairment to a body structure or a body function,
- (v) chronic disease,

(c) foetal distress, foetal death or a congenital physical or mental impairment or birth defect.

Note: planned hospitalization for pre-existing condition, or a procedure required by the CIP, without a serious deterioration of the health status of the subject, is not considered an SAE.

Serious Adverse Device Effect (SADE) (ISO14155)

Adverse device effect (ADE) that has resulted in any of the consequences characteristic of a serious adverse event.

Unanticipated Serious Adverse Device Effect (USADE) (ISO14155)

Serious adverse device effect (SADE) which by its nature, incidence, severity or outcome has not been identified in the current version of the risk analysis report.

Device deficiency with Serious Adverse Device Effect (SADE) potential ((Art. 80 §1 c) MDR; ISO14155)

Any device deficiency that might have led to a serious adverse event if appropriate action had not been taken, intervention had not occurred, or circumstances had been less fortunate.

Serious incident: (Art. 2 § 65MDR)

Means any incident that directly or indirectly led, might have led or might lead to any of the following:

- (a) the death of a patient, user or other person,
- (b) the temporary or permanent serious deterioration of a patient's, user's or other person's state of health,
- (c) a serious public health threat;

Serious public health threat: (Art. 2 § 66MDR)

Event which could result in imminent risk of death, serious deterioration in a person's state of health, or serious illness, that may require prompt remedial action, and that may cause significant morbidity or mortality in humans, or that is unusual or unexpected for the given place and time.

Causal Relationship of SAE (MDCG 2020-10/1)

A causal relationship towards the medical device or the procedure of the investigation should be rated by the PI and the Sponsor as follows:

- e) Not related: The relationship to the device or procedures can be excluded.

- f) Possible: The relationship with the use of the investigational device is weak but cannot be ruled out completely. Alternative causes are also possible.
- g) Probable: The relationship with the use of the investigational device seems relevant and/or the event cannot reasonably be explained by another cause.
- h) Causal relationship: The serious event is associated with the investigational device or with procedures beyond reasonable doubt.

6.2 SAFETY DATA RECORDING

From the "Visite 1 - Day 0" date until patient end of study (i.e., withdrawal/end of follow-up/lost to follow-up), all adverse events (serious and non-serious), exposure during pregnancy and device deficiencies that occur will be fully investigated, recorded and classified by the Investigator in line with the definitions provided in the norm ISO14155:2020 and guideline MEDDEV 2.7/3.

Investigators will check patients file during clinical follow-up visit and ask patients if they experienced any complications since the index procedure / last visit.

Safety data will be reported in the Case Report Form.

Documentation of AEs (including SAEs) by the PI includes diagnosis or symptoms, start and stop dates of event, event treatment, event resolution, assessment of seriousness and causal relationship to Medical Device and/or investigation procedure (ISO14155).

Documentation of DDs by the PI includes description of event, start date, investigational device information, action taken with regard to the investigational device, and whether the DD led to an AE. The Sponsor shall review all DDs and determine and document in writing whether they could.

The Sponsor provides the Competent/Regulatory Authority (CA/RA) (if applicable) and the Ethic Committee (EC/IRB) with the documentation at their request.

6.3 SAFETY DATA REPORTING

6.3.1 Reporting to the Sponsor

The following events are to be reported to the Sponsor by the PI (or authorized designee) without delay and not later than 3 calendar days after becoming aware of the event:

- All SAEs related and unrelated to the studied device
- Health hazards that require measures
- Unanticipated Serious Adverse Device Effect
- Device deficiencies including use error, malfunction, and incident irrespectively of occurrence of AE.

Non serious AE and exposure to the device during pregnancy are transmitted weekly to the sponsor.

Safety data as described above in section 6.1 Definition in addition to exposure during pregnancy are reported in the dedicated form: CRF and vigilance report form provided by the sponsor available in the Investigator Site File and send to the sponsor according to the timelines described above by email to

copy

In case of serious public health threat or in case of death or unanticipated serious deterioration in a person's state of health, the sponsor must be informed immediately by phone (tel: [REDACTED]
[REDACTED] and the dedicated form sent in parallel by email.

A detailed follow-up report containing all additional exams and/or pseudonymized surgical report should be sent to the sponsor as soon as they are available according to the same process and timelines.

The Sponsor will evaluate SAEs with regard to causality and seriousness. Device deficiencies are also assessed regarding their potential to lead to an SAE (DD with SADE potential).

The Sponsor will manage the information on safety according to its procedure.

Reconciliation with the CRO and Septodont medical affairs department are performed in monthly basis with Septodont vigilance department.

Appropriate vigilance training is provided to the CRO.

6.3.2 Reporting to Ethic Committee and Competent/Regulatory Authority

The sponsor will submit the case reports to the Ethic Committee and to Competent/Regulatory Authority as required in the country regulation.

In France:

It is done according to the timelines described in the Article 87 and 90 of the MDR:

- a serious public health threat must be reported immediately and not later than 2 days after the manufacturer becomes aware of that threat
- in the event of death or unanticipated serious deterioration in a person's state of health, the reporting to the CEC must be performed immediately and not later than 10 days after the manufacturer becomes aware of that threat
- in case of any serious incident and after having established the causal relationship between the incident and the device (or such causal relationship is reasonably possible), the reporting to the CEC must be performed immediately and not later than 15 days after the manufacturer become aware.

In India:

All SAE/SADE/USADEs must be reported to the sponsor/legal representative and manufacture within 24 hrs of the investigator team becoming aware of them.

All the SAE/SADE/USADEs will be reported to Institutional Review Board/ Ethics Committee as per local regulatory requirements through an email or telephonically, and Reports of related and unexpected SAEs should be submitted to Ethics Committee within 14 days of the Chief Investigator becoming aware of the event, using the SAE report form.

Full details of the event, treatment, and an assessment of the relationship to study procedures must be provided in the report with detailed information as mentioned in table 7 of Medical Device Rule 2017, DCGI or latest local regulatory requirement.

The Investigator should institute appropriate therapeutic and follow-up measures in accordance with good medical practice but should notify the monitor of such actions and record them in the subject's Case Report Form.

